##### 6.1.1.2. Sensitivity Analyses

- The main analysis is repeated using the copy from reference multiple imputation approach with m=30 imputations to impute missing pain intensity at 2 hours postdose (see Section 5.3).
- The main analysis is repeated by imputing missing data with varying response rates (see Section 5.3).

#### 6.1.2. Percentage of participants with an MBS reported before dosing that is absent at 2 hours postdose

##### 6.1.2.1. Main Analysis

- Estimand strategy: Composite policy (Section 2.2.1).

DMB02-GSOP-RF02 7.0 Statistical Analysis Plan Template 31-Jan-2022

PFIZER CONFIDENTIAL

TMF Doc ID: 98.03

Page 33 of 89

- Analysis set: EAS (Section 4).
- Analysis methodology: The Mantel-Haenszel risk estimation stratified by country/region will be used. See details in Section 5.2.2.
- Intercurrent events and missing data: (1) Taking rescue medication at or before 2 hours postdose (RM=F; see Appendix 2.1) and (2) missing MBS at 2 hours postdose (NC=F; see Section 5.3 for definition) will be regarded as failures.

The same statistics are tabulated as those for the main analysis of pain freedom at 2 hours postdose (see Section 6.1.1.1).

#### 6.1.2.2. Sensitivity Analysis

- The main analysis is repeated using the copy from reference multiple imputation approach with m=30 imputations to impute missing MBS status at 2 hours postdose (see Section 5.3).
- The main analysis is repeated by imputing missing data with varying response rates (see Section 5.3).

### 6.2. Secondary Endpoint(s)

#### 6.2.1. Percentage of participants with a pain intensity of none or mild at 15 minutes postdose

- Estimand strategy: Composite policy (Section 2.2.2).
- Analysis set: EAS (Section 4).
- Analysis methodology: The Mantel-Haenszel risk estimation stratified by country/region will be used. See details in Section 5.2.2.
- Intercurrent events and missing data: (1) Taking rescue medication at or before 15 minutes postdose (RM=F; see Appendix 2.1) and (2) missing pain intensity at 15 minutes postdose (NC=F; see Section 5.3 for definition) will be regarded as failures.

Treatment group comparisons of the percentage of participants with pain relief at 15 minutes postdose (i.e., in the 15-minute postdose analysis window) will present similar statistics as the main analysis of the co-primary endpoint of pain freedom (see Section 6.1.1.1).

#### 6.2.2. Percentage of participants with a pain intensity of none or mild at 30 minutes postdose

- Estimand strategy: Composite policy (Section 2.2.2).
- Analysis set: EAS (Section 4).

- Analysis methodology: The Mantel-Haenszel risk estimation stratified by country/region will be used. See details in Section 5.2.2.
- Intercurrent events and missing data: (1) Taking rescue medication at or before 30 minutes postdose (RM=F; see Appendix 2.1) and (2) missing pain intensity at 30 minutes postdose (NC=F; see Section 5.3 for definition) will be regarded as failures.

Treatment group comparisons of the percentage of participants with pain relief at 30 minutes postdose (i.e., in the 30-minute postdose analysis window) will present similar statistics as the main analysis of the co-primary endpoint of pain freedom (see Section 6.1.1.1).

### 6.2.3. Percentage of participants with a pain intensity of none or mild at 2 hours postdose

- Estimand strategy: Composite policy (Section 2.2.2).
- Analysis set: EAS (Section 4).
- Analysis methodology: The Mantel-Haenszel risk estimation stratified by country/region will be used. See details in Section 5.2.2.
- Intercurrent events and missing data: (1) Taking rescue medication at or before 2 hours postdose (RM=F; see Appendix 2.1) and (2) missing pain intensity at 2 hours postdose (NC=F; see Section 5.3 for definition) will be regarded as failures.

Treatment group comparisons of the percentage of participants with pain relief at 2 hours postdose (i.e., in the 2-hour postdose analysis window) will present similar statistics as the main analysis of the co-primary endpoint of pain freedom (see Section 6.1.1.1).

### 6.2.4. Return to normal function at 2 hours postdose

Return to normal function at a single time point postdose is defined as a functional disability level of normal at that time point for participants with functional disability at the time of dosing.

- Estimand strategy: Composite policy (Section 2.2.2).
- Analysis set: EAS (Section 4). Participants with functional disability at the time of dosing will be included.
- Analysis methodology: The Mantel-Haenszel risk estimation stratified by country/region will be used. See details in Section 5.2.2.
- Intercurrent events and missing data: (1) Taking rescue medication at or before 2 hours postdose (RM=F; see Appendix 2.1) and (2) missing functional disability level at 2 hours postdose (NC=F; see Section 5.3 for definition) will be regarded as failures.

Treatment group comparisons of the percentage of participants with return to normal function at 2 hours postdose (i.e., in the 2-hour postdose analysis window) will present similar statistics as the main analysis of the co-primary endpoint of pain freedom (see Section 6.1.1.1).

#### **6.2.5. Percentage of participants with a pain intensity of none or mild at all time points from 2 to 24 hours postdose**

- Estimand strategy: Composite policy (Section 2.2.2).
- Analysis set: EAS (Section 4).
- Analysis methodology: The Mantel-Haenszel risk estimation stratified by country/region will be used. See details in Section 5.2.2.
- Intercurrent events and missing data: (1) Taking rescue medication at or before 24 hours postdose (RM=F; see Appendix 2.1) and (2) missing pain intensity at 2 or 24 hours postdose (NC=F; see Section 5.3 for definition) and (3) missing pain intensity at >1 time point from 3 to 8 hours postdose (NC1=F; see Section 5.3 for definition) will be regarded as failures.

Treatment group comparisons of the percentage of participants with sustained pain relief from 2 to 24 hours (i.e., in the 2 to 24 hour postdose analysis window) will present similar statistics as the main analysis of the co-primary endpoint of pain freedom (see Section 6.1.1.1).

#### **6.2.6. Percentage of participants with a pain intensity of none or mild at all time points from 2 to 48 hours postdose**

- Estimand strategy: Composite policy (Section 2.2.2).
- Analysis set: EAS (Section 4).
- Analysis methodology: The Mantel-Haenszel risk estimation stratified by country/region will be used. See details in Section 5.2.2.
- Intercurrent events and missing data: (1) Taking rescue medication at or before 48 hours postdose (RM=F; see Appendix 2.1) and (2) missing pain intensity at 2, 24 or 48 hours postdose (NC=F; see Section 5.3 for definition) and (3) missing pain intensity at >1 time point from 3 to 8 hours postdose (NC1=F; see Section 5.3 for definition) will be regarded as failures.

Treatment group comparisons of the percentage of participants with sustained pain relief from 2 to 48 hours (i.e., in the 2 to 48 hour postdose analysis window) will present similar statistics as the main analysis of the co-primary endpoint of pain freedom (see Section 6.1.1.1).

### 6.2.7. Return to normal function at 30 minutes postdose

- Estimand strategy: Composite policy (Section 2.2.2).
- Analysis set: EAS (Section 4). Participants with functional disability at the time of dosing will be included.
- Analysis methodology: The Mantel-Haenszel risk estimation stratified by country/region will be used. See details in Section 5.2.2.
- Intercurrent events and missing data: (1) Taking rescue medication at or before 30 minutes postdose (RM=F; see Appendix 2.1) and (2) missing functional disability level at 30 minutes postdose (NC=F; see Section 5.3 for definition) will be regarded as failures.

Treatment group comparisons of the percentage of participants with return to normal function at 30 minutes postdose (i.e., in the 30-minute postdose analysis window) will present similar statistics as the main analysis of the co-primary endpoint of pain freedom (see Section 6.1.1.1).

### 6.2.8. Return to normal function at 60 minutes postdose

- Estimand strategy: Composite policy (Section 2.2.2).
- Analysis set: EAS (Section 4). Participants with functional disability at the time of dosing will be included.
- Analysis methodology: The Mantel-Haenszel risk estimation stratified by country/region will be used. See details in Section 5.2.2.
- Intercurrent events and missing data: (1) Taking rescue medication at or before 60 minutes postdose (RM=F; see Appendix 2.1) and (2) missing functional disability level at 60 minutes postdose (NC=F; see Section 5.3 for definition) will be regarded as failures.

Treatment group comparisons of the percentage of participants with return to normal function at 60 minutes postdose (i.e., in the 60-minute postdose analysis window) will present similar statistics as the main analysis of the co-primary endpoint of pain freedom (see Section 6.1.1.1).

### 6.2.9. Freedom from phonophobia at 2 hours postdose

Freedom from phonophobia at a single time point postdose is defined as phonophobia absent at that time point for participants with the phonophobia present at the time of dosing.

- Estimand strategy: Composite policy (Section 2.2.2).

- Analysis set: EAS (Section 4). Participants with phonophobia present at the time of dosing will be included.
- Analysis methodology: The Mantel-Haenszel risk estimation stratified by country/region will be used. See details in Section 5.2.2.
- Intercurrent events and missing data: (1) Taking rescue medication at or before 2 hours postdose (RM=F; see Appendix 2.1) and (2) missing phonophobia status at 2 hours postdose (NC=F; see Section 5.3 for definition) will be regarded as failures.

Treatment group comparisons of the percentage of participants with phonophobia freedom at 2 hours postdose (i.e., in the 2-hour postdose analysis window) present similar statistics as the main analysis of the co-primary endpoint of pain freedom (see Section 6.1.1.1).

#### 6.2.10. Freedom from photophobia at 2 hours postdose

Freedom from photophobia at a single time point postdose is defined as photophobia absent at that time point for participants with the photophobia present at the time of dosing.

- Estimand strategy: Composite policy (Section 2.2.2).
- Analysis set: EAS (Section 4). Participants with photophobia present at the time of dosing will be included.
- Analysis methodology: The Mantel-Haenszel risk estimation stratified by country/region will be used. See details in Section 5.2.2.
- Intercurrent events and missing data: (1) Taking rescue medication at or before 2 hours postdose (RM=F; see Appendix 2.1) and (2) missing photophobia status at 2 hours postdose (NC=F; see Section 5.3 for definition) will be regarded as failures.

Treatment group comparisons of the percentage of participants with photophobia freedom at 2 hours postdose (i.e., in the 2-hour postdose analysis window) present similar statistics as the main analysis of the co-primary endpoint of pain freedom (see Section 6.1.1.1).

#### 6.2.11. Freedom from nausea at 2 hours postdose

Freedom from nausea at a single time point postdose is defined as nausea absent at that time point for participants with the nausea present at the time of dosing.

- Estimand strategy: Composite policy (Section 2.2.2).
- Analysis set: EAS (Section 4). Participants with nausea present at the time of dosing will be included.
- Analysis methodology: The Mantel-Haenszel risk estimation stratified by country/region will be used. See details in Section 5.2.2.

- Intercurrent events and missing data: (1) Taking rescue medication at or before 2 hours postdose (RM=F; see [Appendix 2.1](#)) and (2) missing nausea status at 2 hours postdose (NC=F; see [Section 5.3](#) for definition) will be regarded as failures.

Treatment group comparisons of the percentage of participants with nausea freedom at 2 hours postdose (i.e., in the 2-hour postdose analysis window) present similar statistics as the main analysis of the co-primary endpoint of pain freedom (see [Section 6.1.1.1](#)).

#### **6.2.12. Percentage of participants with a pain intensity of none at all time points from 2 to 24 hours postdose**

- Estimand strategy: Composite policy ([Section 2.2.2](#)).
- Analysis set: EAS ([Section 4](#)).
- Analysis methodology: The Mantel-Haenszel risk estimation stratified by country/region will be used. See details in [Section 5.2.2](#).
- Intercurrent events and missing data: (1) Taking rescue medication at or before 24 hours postdose (RM=F; see [Appendix 2.1](#)) and (2) missing pain intensity at 2 or 24 hours postdose (NC=F; see [Section 5.3](#) for definition) and (3) missing pain intensity at >1 time point from 3 to 8 hours postdose (NC1=F; see [Section 5.3](#) for definition) will be regarded as failures.

Treatment group comparisons of the percentage of participants with sustained pain freedom from 2 to 24 hours (i.e., in the 2 to 24 hour postdose analysis window) will present similar statistics as the main analysis of the co-primary endpoint of pain freedom (see [Section 6.1.1.1](#)).

#### **6.2.13. Percentage of participants with a pain intensity of none at all time points from 2 to 48 hours postdose**

- Estimand strategy: Composite policy ([Section 2.2.2](#)).
- Analysis set: EAS ([Section 4](#)).
- Analysis methodology: The Mantel-Haenszel risk estimation stratified by country/region will be used. See details in [Section 5.2.2](#).
- Intercurrent events and missing data: (1) Taking rescue medication at or before 48 hours postdose (RM=F; see [Appendix 2.1](#)) and (2) missing pain intensity at 2, 24 or 48 hours postdose (NC=F; see [Section 5.3](#) for definition) and (3) missing pain intensity at >1 time point from 3 to 8 hours postdose (NC1=F; see [Section 5.3](#) for definition) will be regarded as failures.

Treatment group comparisons of the percentage of participants with sustained pain freedom from 2 to 48 hours (i.e., in the 2 to 48 hour postdose analysis window) will present similar

statistics as the main analysis of the co-primary endpoint of pain freedom (see Section 6.1.1.1).

#### 6.2.14. Percentage of participants with pain relapse at any time point after 2 hours postdose

Pain relapse at any time point after 2 hours postdose is defined as pain intensity of mild, moderate, or severe at any time point after 2 hours postdose for participants with pain intensity of none at 2 hours postdose.

- Estimand strategy: Composite policy (Section 2.2.2).
- Analysis set: EAS (Section 4). Participants with pain freedom at 2 hours postdose will be included.
- Analysis methodology: The Mantel-Haenszel risk estimation stratified by country/region will be used. See details in Section 5.2.2.
- Intercurrent events and missing data: (1) Taking rescue medication at or before 48 hours postdose (RM=F; see Appendix 2.1) and (2) missing pain intensity at >1 time point from 3 to 48 hours postdose (NC1=F; see Section 5.3 for definition) will be regarded as failures.

Treatment group comparisons of the percentage of participants with pain relapse at any time point after 2 hours postdose (i.e., in the 3 to 48 hour postdose analysis window) will present similar statistics as the main analysis of the co-primary endpoint of pain freedom (see Section 6.1.1.1).

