##### Pain Freedom over Time

At time point X, participants who meet both of the following criteria are classified as responders:

- Pain intensity of none at X, i.e., in the X analysis window
- No rescue medication taken at or before the pain intensity assessment in the X analysis window.

At time point X, participants who are not responders are classified as failures. Failure criteria include any of the following:

- Rescue medication taken at or before X (RM=F)
- Mild, moderate, or severe pain intensity at X
- Missing pain intensity at X (NC=F).

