### **Pain Relapse from 2 to 48 Hours Postdose**

Pain relapse from 2 to 48 hours postdose is defined as pain intensity of mild, moderate, or severe at any time point after 2 hours postdose for the subset of participants with pain freedom (i.e., pain intensity of none) at 2 hours postdose.

Participants who meet all the following criteria are classified as non-relapsers:

- Pain intensity of none at all time points after 2 hours postdose, i.e., in the 3 to 48-hour postdose analysis windows
- No rescue medication taken at or before the pain intensity assessment in the 48-hour postdose analysis window.

Participants who are not non-relapsers are classified as relapsers. Relapse criteria include any of the following:

- Rescue medication taken at or before 48 hours postdose (RM=F)
- Mild, moderate, or severe pain intensity at any time point after 2 hours postdose, i.e., in the 3, 4, 6, 8, 24, or 48-hour postdose analysis window

- Missing pain intensity at any time point after 2 hours postdose (NC=F), i.e., in the 3, 4, 6, 8, 24, or 48-hour postdose analysis window.

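### The SAP gives two incompatible at-risk sets for pain relapse, and under one of them rescue taken before 2 hours is scored as a relapse

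*SAP*

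**What the plan says.** The at-risk set is described in two ways.

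- **By pain intensity alone.** The definition sentence of SAP 6.2.14 places relapse "at any time point after 2 hours postdose for participants with pain intensity of none at 2 hours postdose". The derivation in Appendix 2.1.1 (Pain Relapse from 2 to 48 Hours Postdose) states it "for the subset of participants with pain freedom (i.e., pain intensity of none) at 2 hours postdose". Neither mentions rescue as a condition of entry.
- **By pain freedom.** The analysis-set line of SAP 6.2.14 reads "Participants with pain freedom at 2 hours postdose will be included". Appendix 1 and the estimand populations (SAP 2.2.2, Protocol 9.1.1.2) use the same term. Appendix 2.1.1 (Pain Freedom over Time) derives that term for any time point X. A responder needs a pain intensity of none and also "No rescue medication taken at or before the pain intensity assessment in the X analysis window".

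The rescue criterion for relapse is the same in both places. It covers any rescue up to 48 hours and has no starting time: the derivation lists "Rescue medication taken at or before 48 hours postdose (RM=F") among the relapse criteria. The default class is relapse: "Participants who are not non-relapsers are classified as relapsers".

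**The concern.** Relapse is meant to measure what happens after 2 hours in people whose pain had gone by 2 hours. If entry rests on pain intensity alone, someone who took rescue before 2 hours can enter. The same early rescue then makes that person a relapser, although it came before the period being measured and no pain returned. The relapse denominator would also exceed the number of pain-freedom responders reported for the co-primary endpoint. Two programmers working from different lines of the SAP could produce different denominators and different relapse percentages.

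**Working it through.** **The plan's own figures.** The documents give no figure for relapse. The rates used below come from Protocol 9.5: 630 per group, pain freedom 23.2% v 15.1%, MBS freedom 40.5% v 32.1%, 2-sided alpha 0.05. With power = Φ(|p1 − p2|/SE − 1.96) and SE = √(p1(1−p1)/n + p2(1−p2)/n), they give 95.7% and 87.5%, as stated. The product is 0.957 × 0.875 = 83.7%, against a stated 84% or so. This point does not change those figures.

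**One participant traced through both definitions.** Rescue at 90 minutes (time recorded); pain none at 2 hours and at every later assessment to 48 hours; no missing entries, so the missing-data rules play no part.

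| Step | Entry by pain intensity | Entry by pain-freedom derivation |
|---|---|---|
| Co-primary at 2 hours | Failure (early rescue) | Failure (early rescue) |
| In relapse denominator? | Yes | No |
| Relapse status | Relapser, through the rescue criterion | Not assessed |

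**Size.** Let N be the 2-hour responders in an arm, r their relapse rate, and k the participants with rescue before the 2-hour assessment and pain none at it. Under the derivation the relapse rate is r. Under the pain-intensity wording all k enter and all are scored as relapsers, so the rate is (rN + k)/(N + k), an excess of k(1 − r)/(N + k).

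N = 630 × 0.232 = 146.16 for zavegepant and 630 × 0.151 = 95.13 for placebo, assuming the planning rates already count early rescue as failure. Neither r nor k is in the documents, so both are assumed. Differences are taken before rounding.

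| r | k (zavegepant / placebo) | Zavegepant | Placebo | Difference (points) |
|---|---|---|---|---|
| any | 0 / 0 | r | r | 0 |
| 40% | 2 / 2 | 40.8% | 41.2% | −0.4 |
| 40% | 6 / 6 | 42.4% | 43.6% | −1.2 |
| 40% | 3 / 6 | 41.2% | 43.6% | −2.4 |
| 40% | 4 / 2 | 41.6% | 41.2% | +0.4 |
| 30% | 5 / 5 | 32.3% | 33.5% | −1.2 |
| 30% | 5 / 10 | 32.3% | 36.7% | −4.3 |
| 50% | 5 / 5 | 51.7% | 52.5% | −0.8 |
| 50% | 5 / 10 | 51.7% | 54.8% | −3.1 |

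**Plausible k.** If 1% to 5% of an arm took rescue before 2 hours and 15% to 25% of those reported no pain (both assumed), k runs from 630 × 0.01 × 0.15 = 0.9 to 630 × 0.05 × 0.25 = 7.9. The 5 / 10 rows go beyond that range.

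**Direction.** The excess is equal in the two arms when k/N is equal, that is when zavegepant has 146.16/95.13 = 1.54 times as many cases as placebo. Below that ratio the difference leans towards zavegepant; above it, towards placebo.

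**Against sampling error.** At r = 40% in both arms, SE = √(0.4 × 0.6 × (1/146.16 + 1/95.13)) = 6.5 points, so the 95% CI half-width is about 12.6 points.

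**The case against.** A reader might infer that the SAP simply admits everyone with no pain at 2 hours and counts early rescue users as relapsers. The documents do not settle on that. The analysis-set line, Appendix 1 and both estimand populations say pain freedom, and on the formal derivation the 90-minute rescue user never enters. The gloss in the relapse derivation may be shorthand: the SAP describes the co-primary endpoint in the same pain-only terms and still treats rescue by 2 hours as failure. This stands, and it is why the finding is a conflict between two definitions.

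It does not remove the problem. The gloss sits inside the relapse derivation itself, next to the rule it feeds, and says there what the term means. That is the text a programmer would most naturally code from. Elsewhere in Appendix 2.1.1 the shorthand is completed by a rescue condition that fits the endpoint. Here the only rescue condition governs relapse status, not entry.

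It is also fair that the affected group should be small. Protocol 6.9.2 and 8.2.3 prohibit rescue in the first 2 hours, so a timed case needs a deviation. The group can still exist, because Protocol 6.9.2 keeps diary entries going after rescue and the SAP's rescue algorithm covers time points from 15 minutes onward.

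**Conclusion.** The point holds as a conflict in the SAP: two at-risk sets are stated, and one of them misclassifies participants whose pain never returned. The relapse percentage is inflated in any arm that has such cases.

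The size cannot be found from the documents. With 2 to 6 cases per arm, split evenly or up to two to one, the between-arm difference moves by roughly 0 to 2 points, well inside the sampling error. A larger or more lopsided split would move it further, and with no cases there is no effect.

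A reader might also infer a bias in favour of zavegepant, because the placebo denominator is smaller. That follows for equal counts but not in general, and nothing in the documents says how cases would split.

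The co-primary and key secondary tests are untouched. Under SAP 5.1, relapse is an other secondary endpoint, unadjusted and descriptive.

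**What to change.** In SAP 6.2.14, Appendix 1 and Appendix 2.1.1, define the relapse subset as the 2-hour responders under Pain Freedom over Time. Delete the parenthetical gloss in the relapse derivation and the matching pain-intensity wording in the 6.2.14 definition sentence.

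A separate limit to rescue after 2 hours is then unnecessary, since nobody in the subset has an earlier first rescue. The estimand's 48-hour rescue wording can stay as it is.

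The cost is a few words and one programming condition, because the responder flag already exists. There is one small downside. When the rescue time is missing, the algorithm in Appendix 2.1.2 compares dates only, so untimed rescue on the day of the 2-hour assessment counts as taken by that assessment. Those participants leave the relapse subset even if the rescue came later. Report their number by arm.
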